Use liver biopsy as “golden standard” for pathological staging, to evaluate the clinical values of FibroTouch for the non-invasive and quantitative diagnosis of liver fibrosis and cirrhosis in CHB patients.

(II) Secondary Objective

- ◆ Difference between FibroTouch and FibroScan in the rate of d successful detection
- ◆ Difference between FibroTouch and FibroScan in the determined values
- ◆ Correlation between determined values of FibroTouch and ultrasonic semi-quantitative scores
- ◆ Performance of FibroTouch.

- Positioning accuracy evaluated by investigators
- Image displaying ability evaluated by investigators
- Scanning speed evaluated by investigators
- Detecting and calculating speed evaluated by investigators

III. Study Goal

To determine the diagnostic accuracy, specificity and sensitivity of FibroTouch for liver fibrosis assessment in CHB patients.

IV. Study Type

It's a prospective and multicenter study.

V. Anticipated Total Cases

According to publications on FibroScan and liver biopsy examination, the mean sensitivity and specificity are 0.61 and 0.90 respectively for different stages (four pathological stages: $\geq F4$, $\geq F3$, $\geq F2$ and F0-F1). Assuming a similar sensitivity and specificity of FibroScan and FibroTouch, the lowest clinically acceptable sensitivity and specificity is 0.55

and 0.8 respectively, when $\alpha=0.05$ and power=80%, 423 cases are required based on sensitivity; total 529 cases are required based on the determination effectiveness=80%; 328 cases are required based on specificity; total 410 cases are required based on the determination effectiveness=80%. By considering the center assignment, ≥ 600 qualified cases are included to guarantee 500 final statistical cases; and ≥ 100 cases are required for S0+S1, S2, S3, S4 and liver cirrhosis (compensatory stage) respectively. For each stage, the case is assigned as equally as possible.

VI. Study Time

One year (from May 2014 to May 2015).

VII. Case Assignment System (via central registration system)

Subject No. is assigned through IWRS system. After the investigator logs in the system and fills in the pathological stages, this system will, according to the completed contents, automatically assign the sole subject No. for this subject.

VIII. Statistical Analysis

Peking University Clinical Research Institute

IX. Study Design

(I) Inclusion Criteria

1. Age: 18—65 years, both gender.
2. History of HBV or HBsAg positive > 6 months up to now.

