◆ By grouping according to the grading result via golden standard, the inter-group comparison is made on the FibroTouch determination results through the variance analysis or Wilcoxon rank-sum test, the correlation between two groups is tested through the Spearman correlation analysis, and the correlation coefficient (r) and 95% CI are calculated for two groups.

◆ By regarding the different grading results of golden standard as the judgment critical point, the curve of receiver operating characteristic (ROC) for elasticity value is constructed. The subjects are grouped by regarding the different determination results of elasticity value as the judgment critical point, the sensitivity/specificity is calculated according to the grading result of golden standard, the ROC curve is plotted through the X-axis of specificity, the Y-axis of sensitivity and the calculated result, and the area under curve and its 95% confidence interval are calculated. The critical value corresponding to whichever is greater for the result of sensitivity and specificity is regarded as the judgment critical point for FibroTouch determination value, and then the corresponding sensitivity, specificity, positive predicted value and negative predicted value are calculated.

Comparison of secondary objective: by statistically assuming the success rate of FibroTouch is non-inferior to that of Fibroscan, the critical value of non-inferiority is 10%; and by statistically assuming the determination result of FibroTouch is equivalent to that of Fibroscan, the critical value of equivalence is 1.5KPa.

In the above analysis, $P < 0.05$ indicates a significant difference.

(VIII) Data Management and Data Traceability

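### Section V's 423 cases imply an undeclared one-sided 5% test counted in target-stage patients, and the stage quotas do not deliver the stated 80% power for sensitivity on either reading of alpha

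*Combined protocol and SAP*

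**What the plan says.** Section V (Anticipated Total Cases) takes its expected values from published FibroScan work: "the mean sensitivity and specificity are 0.61 and 0.90 respectively for different stages". It sets floors: "the lowest clinically acceptable sensitivity and specificity is 0.55" for sensitivity, and 0.8 for specificity. With alpha at 0.05 and power at 80%, it then states: "423 cases are required based on sensitivity". Sidedness is not given. The number is next enlarged for unusable measurements: "total 529 cases are required based on the determination effectiveness=80"%. The specificity figures are 328 and 410.

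The plan settles on at least 600 included patients so as to have 500 in the final analysis. It asks for at least 100 in each of five groups (S0+S1, S2, S3, S4 and compensated cirrhosis), as equal as possible.

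Section IX (VII) (Statistical Analysis of Data) gives a 95% interval for the correlation coefficient and for the ROC area ("the area under curve and its 95% confidence interval are calculated"). Sensitivity and specificity at the chosen cut-off are to be calculated, with no interval and no comparison with 0.55 or 0.8. The only general decision rule is: "In the above analysis, $P < 0.05$ indicates a significant difference".

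**The concern.** A sample size is tied to a test. If section V assumed one tail at 5% and the results are later judged by an ordinary two-sided 95% interval, the stated 80% power does not belong to the rule applied. Because neither section names that rule, the interval level could also be chosen after the results are seen.

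A second question comes with it: whom do the 423 cases count? Sensitivity is estimated only in patients who have the target stage. If 423 is a number of such patients, 500 patients spread over five stage groups may not contain that many at any threshold, whichever tail is used.

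**Working it through.** **Inputs.** From section V: p1 = 0.61, p0 = 0.55, alpha 0.05, power 80%, 500 final cases, five groups of about 100. From the analysis section: 95% intervals and P<0.05, with sidedness not written.

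**Step 1: reproduce 423.** For an exact one-sample binomial test of p0 against p1, find the smallest n with power of at least 80%.

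- One-sided 0.05: n = 423. Reject at 250 or more positives; actual alpha 0.0495, power 0.803. This matches the plan exactly.
- 0.025 per tail: n = 538. Reject at 319 or more; actual alpha 0.0248, power 0.804.

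Exact power is a saw-tooth in n, so these are the first sizes to reach 80%. Power stays above 80% only from 447 and 562 respectively.

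**Step 2: check by normal approximation.** n = [(z_alpha·√(p0·q0) + z_beta·√(p1·q1)) / (p1 − p0)]², with √(0.55×0.45) = 0.4975 and √(0.61×0.39) = 0.4877.

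- One-sided: [(1.645×0.4975 + 0.842×0.4877)/0.06]² = 419.4, so 420.
- Two-sided: [(1.960×0.4975 + 0.842×0.4877)/0.06]² = 533.3, so 534.

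Other variants (null or alternative variance only, arcsine, continuity correction) give 409 to 442 one-sided and 519 to 557 two-sided. No two-sided variant comes near 423.

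**Step 3: power at 423 with 0.025 per tail.**

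- Exact: reject at 254 or more; power 0.675.
- Normal approximation: Φ[(0.06×√423 − 1.960×0.4975)/0.4877] = Φ(0.53) = 0.702.

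**Step 4: how many patients count.** With 500 split equally over the five groups, the number at or above a threshold is 400 (S2 up), 300 (S3 up) or 200 (S4 plus cirrhosis). This takes the S stages of the quotas as matching the F stages used earlier in section V, and counts compensated cirrhosis with S4.

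| Threshold | Positives of 500 | Exact power, one-sided 0.05 | Exact power, 0.025 per tail |
|---|---|---|---|
| Stage 2 or above | 400 | 78% | 68% |
| Stage 3 or above | 300 | 66% | 53% |
| Stage 4 or above | 200 | 47% | 36% |

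No threshold reaches 423. In a four-fifths split, 423 positives would need 423/0.8 = 529 evaluable patients, which is more than 500. The plan's own 529 is the same division, but there the 0.8 is the effective-determination rate. Section V shows no separate step for stage mix.

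**Step 5: specificity as a cross-check.** For 0.90 against 0.80, the exact test first reaches 80% power at 82 negatives one-sided and 107 at 0.025 per tail. Since 4 × 82 = 328, the plan's figure fits a one-sided test if 25% of patients are negative. That 25% is an assumption worked back from the result. The documents do not state it, and equal quotas would give 20% at the stage 2 threshold. At that threshold about 100 negatives are expected, enough for 82 but not for 107.

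**The case against.** The strongest reply is that section V contains no arithmetic error. A lowest acceptable value is a floor, the question is directional, and a one-sided 5% test is an ordinary choice for which 423 is right. This stands. What is missing is the statement of it.

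A reader might go further and infer that the analysis section prescribes a two-sided test which contradicts the sample size. The documents do not support that. They never write two-sided. Their 95% intervals belong to the correlation coefficient and the ROC area, and sensitivity is only calculated. The P<0.05 sentence is general and also follows a non-inferiority hypothesis with a 10% margin, which is directional. The two-sided figures here therefore describe what happens under a conventional reading, not a rule that the plan sets.

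It can also be said that 500 is a minimum. The background section cites 99% effective detection for FibroTouch. If nearly all of 600 patients were evaluable and four-fifths were at S2 or above, there would be about 475 to 480 positives, with exact power near 83% one-sided and 75% two-sided. This is fair for the lowest threshold with one tail. But at the plan's own 80% rate, 600 gives 480 evaluable and 480 × 0.8 = 384 positives. At stage 3 or above, even 600 fully evaluable patients in equal groups give 600 × 3/5 = 360, still short of 423.

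Finally, section V says only cases, so reading 423 as target-stage patients is an inference. It rests on the exact match in Step 1 and on the fact that a test of sensitivity uses only such patients.

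**Conclusion.** The point holds as a power statement that the design does not deliver, together with an undeclared sidedness. It does not hold as a contradiction between two stated tests, nor as a miscalculated 423.

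For sensitivity 0.61 against 0.55, the stated 80% belongs to 423 target-stage patients and a one-sided 5% test. Under the plan's 500 final cases and near-equal quotas, the best threshold gives about 78% one-sided. That is a small shortfall, but it grows to 66% and 47% at the higher thresholds. With 0.025 per tail the figures are 68%, 53% and 36%.

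These results assume equal groups, stage-by-stage correspondence of S and F, and the same 0.61 and 0.55 at every threshold, as section V's averaged inputs imply. More than 500 evaluable patients, or a mix weighted towards higher stages, would raise them.

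**What to change.** In section V, state that 423 counts patients with the target stage and that alpha is one-sided 5%. Replace the single 80% for sensitivity with power per threshold at the quota numbers (about 78%, 66% and 47% for 400, 300 and 200 positives).

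In the analysis section, add the matching rule: a one-sided 95% lower confidence bound, which is the lower limit of the two-sided 90% interval, for sensitivity against 0.55 and specificity against 0.80.

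Alternatively, keep a two-sided 95% interval for both measures and restate sensitivity power as about 68% at best under the quotas. In that case also note that specificity would need 107 negatives, where about 100 are expected at the stage 2 threshold.

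Either choice is a change of wording and needs no extra patients. The cost is a less favourable stated power.

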3. With qualified liver biopsy within three months before or after Fibrotouch examination for pathological staging.
4. Without chemical therapy history of powerful medicine to lower enzyme in the two weeks before blood biochemistry tests (e.g. dimethyl diphenyl bicarboxylate and bicyclol).
5. Participant agreed and signed the informed consent form.

(II) Exclusion Criteria

1. The people who are unable or unwilling to sign informed consent form.

2. The people who have merger of hepatitis c, alcohol and non-alcoholic fatty liver disease, autoimmune liver disease, inherited metabolic liver disease, biliary systemic disease or liver and gall parasitic diseases.
3. The people who have other serious chronic disorders or history of malignancy.
4. The people with ALT ≥ 5 ULN in the past 1 month.
5. The people with $WBC < 3.5 \times 10^9/L$, $PLT < 60 \times 10^9/L$, $PTA < 60\%$.
6. The people with $DBIL \geq 1.5$ ULN.
7. The people with decompensated cirrhosis (especially the people with ascites).
8. Pregnant or lactating women, or women who has a pregnant plan and don't want to birth control in the study period.
9. The people who have wound on the right upper abdomen recently.
10. The people who have various space-occupying tumor or cyst in right liver.
11. The people who have none or limited legal capacity.

(III) Study method

1. Outpatients and inpatients with chronic hepatitis B and compensatory liver cirrhosis, conforming to the inclusion criteria and signing the ICF.
2. Collection of materials and specimen:
 - ◆ Collection of clinical materials: Fill in the uniformly-printed CRF and keep or duplicate the original medical record.
 - (1) Name, sex, age, illness course, family history of infectious diseases and hereditary diseases, drinking history, pharmacotherapy history, and history of chronic diseases (e.g. essential hypertension, heart disease and diabetes).
 - (2) Physical examination: Height (cm), weight (kg), body mass index ($BMI = \text{weight}/\text{height}^2$), heart rate (bpm), respiratory rate (times/min), blood pressure (mmHg).
 - ◆ Retaining of hematological specimen: Within one week before the FibroTouch examination, the venous blood is drawn at an empty stomach, and the different portions of

blood are kept: 2ml whole blood (freeze in two 2ml tubes); 8ml completely-separated serum (freeze in four 2ml tubes); and 3ml plasma (freeze in two 2ml tubes). Keep the tube at -80°C, and uniformly send it to the central laboratory.

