◆ Retaining of liver puncture specimen: Fix with 10% neutral formalin, retain additionally 6 white films at every unit, and send it to the pathological examination center (the quality control is shown in Appendix 1).

3. Hematological examination: (the quality control is shown in Appendix 1)

(1) Routine blood tests;

(2) PT, PTA, INR;

(3) TP, ALB, AST, ALT, CHE, GGT, ALP, TBA, TBIL, DBIL, GLU, TC, TG, HDL, LDL, BUN, Cr;

(4) AFP;

(5) Serum virological indices: hepatitis B test (five-item), HBV-DNA assay, HCV antibody test, HIV antibody test; HDV antigen test.

4. Ultrasonic examination:

Within three months after the liver biopsy, the ultrasonic examination is made at an empty stomach for ≥ 8 h. The inner diameter of liver, spleen, gallbladder, portal vein and splenoportal vein is measured through the ordinary two-dimensional ultrasonic examination. The echo data of liver surface/edge/parenchyma and gallbladder wall is scored to evaluate the severity of fibrosis. At every center, the operation should be made via the fixed machine by the fixed person, so as to prevent the artificial error; and the ultrasonic examination, the elasticity determination of liver tissues and the collection of medical history should be made in the same day.

Semi-quantitative Scoring Criteria at Liver Ultrasonic Examination

Score Item	1 score	2 scores	3 scores
Liver surface (Ls)	Smooth, flat	Unsmooth, fine water ripple	Wave, saw-shaped or discontinuous
Liver parenchyma (Lp)	Fine spot, uniform distribution	Slightly enhanced, coarse particle of non-uniform	Obviously echo enhanced, particulate or nodular echo group

		distribution	
Gallbladder wall (G)	Smooth	Coarse, slightly thickened	Obviously thickened or two-side sign

5. Liver Stiffness Measurement (LSM)

Within 3 months before and after the liver biopsy, the liver stiffness measurement (LSM) values are determined via FibroTouch.

◆ Investigators will operate the FibroTouch system to measure the patients' values of liver stiffness and fat attenuation parameters according to the SOP of FibroTouch.

<1>. Subjects lie in face-up position, and stretch his or her right arm to the maximum extent or cross behind his or her head. Enter the name, gender, birth date, medical card No., height, weight and other information into patient information log in FibroTouch system.

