<2>. In order to determine accurately, image-guided positioning with ultrasonic B probe should be performed prior to the scanning with liver fibrosis probe. Apply ultrasonic coupling agent to the patient's skin at the position of right side, interspace between the Seventh and eighth rib along the midaxillary line, place the ultrasonic B probe perpendicularly on the skin, and then turn on the FibroTouch image-guided scanning model. Investigator can choose the proper position for liver examination with reference to the ultrasonic B image on the video display screen.

The testing position (at the center line of ultrasonic B image) is selected as following roles:

1. Be away from the heterogeneous liver tissues, such as great vessels, cysts and nodes.
2. Be away from the edge of liver.
3. The position where liver tissue are homogeneous, well-proportioned and with thickness no less than 7cm.

<3>. Save the ultrasonic B image, hang off ultrasonic B probe from the selected position, and change to liver fibrosis scanning model. Hold the fibrosis scanning probe in right hand, bend forefinger to keep probe perpendicularly at the selected position on the skin, lie right elbow on the bed (to avoid the right arm from shaking and moving), and left hand hold the tail of the probe to control the direction. Press the probe slightly on patients' skin to make the pressure indicating strip turn green.

<4>. With subject holding his or her breath slightly, operator observes the liver tissue displayed by ultrasonic-M signal. When the tissue is dark, more homogeneous and laminar distribution, the operators can press down the foot switch, and the fibrosis scanning probe sent out low-frequency shear waves for diagnosing and ultrasonic waves for monitoring, the probe is activated and complete once examination of LSM.

<5>. Ten times of successful detection are performed at the same position. When the inter

quartile range (IQR) value is qualified, the median value of these detections will be considered as the examination result of LSM.

<6>. Save and print the test result.

◆ The operator of FibroTouch must be trained by Hisky and obtain an operating license or certificate.

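### The visible plan does not mask the FibroTouch operator to the biopsy stage, although the site may hold that stage when the scan is made

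*Combined protocol and SAP*

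**What the plan says.** **Registration.** Section VII assigns the subject number "After the investigator logs in the system and fills in the pathological stages". Section V asks for at least 100 cases in each of five stage groups and adds: "For each stage, the case is assigned as equally as possible". The site therefore handles the stage as part of enrolment.

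**Who scans, and with what discretion.** Section IX (III) item 5 states: "Investigators will operate the FibroTouch system to measure the patients' values of liver stiffness". Step <2> adds: "Investigator can choose the proper position for liver examination with reference to the ultrasonic B image". In step <4> the operator judges the M-signal picture and triggers the measurement by foot switch. The later bullets of item 5 set signal-quality requirements, limit the IQR-to-median ratio to 0.3 and require repetition when a result is not reliable. They also require one fixed operator per site, as a measure against artificial errors.

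**Order of the tests.** Inclusion criterion 3 reads: "With qualified liver biopsy within three months before or after Fibrotouch examination for pathological staging". Item 5 likewise allows both orders: "Within 3 months before and after the liver biopsy, the liver stiffness measurement (LSM) values are determined via FibroTouch". Item 4 is narrower: "Within three months after the liver biopsy, the ultrasonic examination is made at an empty stomach", and "the ultrasonic examination, the elasticity determination of liver tissues and the collection of medical history should be made in the same day". Item 7 places the biopsy within the 3 months before FibroTouch.

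**Pathology.** Item 7 has HE staining done at every unit, further unstained sections sent to the central laboratory, and three pathologists reading independently with a Kappa check. Appendix 1 gives the final evaluation to three experts.

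**The concern.** The study goal in Section III is the accuracy of FibroTouch, including its sensitivity and specificity, and the primary objective makes biopsy the reference standard. Such estimates are trustworthy only if the index test is made without knowledge of the reference result, and the reference is read without knowledge of the index test. Someone who knows that a patient has cirrhosis may, without intending it, settle on a stiffer position, trigger at a different moment, or be readier to call a set unreliable and repeat it. If that happens differently by stage, the separation between stages is distorted, most plausibly in the device's favour.

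The timing also matters. Once scans and readings are done, masking cannot be restored. A later comparison of accuracy by test order would be possible only if both orders occur, and it would be confounded by whatever determined the order.

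**Working it through.** No arithmetic settles this point, and the plan gives no figure to reproduce. The check sets the sections side by side.

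1. **Is masking stated anywhere?** No visible section masks the operator to the stage or the pathologists to the stiffness value. The nearest statements do other work. The trained, fixed operator in item 5 concerns skill and consistency. Independent reading in item 7 concerns the three readers' independence of one another. Section IX (VIII) 8.7 uses a word at database lock that may be a misprint for unblinded, but it does not say who was masked to what.

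2. **Can the stage exist before the scan?** Yes. Item 7 puts biopsy before FibroTouch. Item 4 puts ultrasound after biopsy and elasticity on the same day as ultrasound, so elasticity also follows biopsy. Stage entry (Section VII) and local HE staining (item 7) show where a stage could be held at the site.

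3. **Can the operator be someone who knows it?** Possibly. Section VII names the investigator as the person who enters the stage, and item 5 names investigators as the people who scan. Nothing separates the two roles. Nothing says that they coincide either.

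4. **Could knowledge affect the result?** The position rules, the median of ten acquisitions, the signal requirements and the 0.3 limit narrow the operator's influence. They do not remove it: position and trigger remain choices, the signal requirements are partly visual, and the 0.3 limit controls spread within a set rather than which set is kept.

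5. **Which distortion would matter?** Section IX (VII) derives the cut-off from the study's own ROC curve. A shift of all readings by the same amount moves the cut-off with them and leaves AUC, sensitivity and specificity unchanged. Only a shift that differs by stage matters.

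6. **Does an analysis deal with it?** None in the visible text. Section IX (VII) says that a statistical analysis plan is to be prepared after the protocol is settled; no separate plan of that kind is visible.

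7. **The reverse direction.** Under criterion 3 and item 5 the scan may come first, so a stiffness value may exist when slides are read. No section passes it to a reader. The specimen-bottle label in Appendix 1 carries a name abbreviation, department and case number, and no stiffness value. No coding of slides is described.

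**The case against.** The strongest reply is that this is silence, not exposure. Nothing places registration before the scan. Item 5 step <1> logs the scan under name, gender, birth date, medical card number and similar details; the subject number is not listed, so on the visible text a scan need not wait for registration. Local HE staining shows that a slide exists at the site, not that a stage is reported to the operator. Appendix 2 (the flow chart) and the FibroTouch SOP are not visible and might set masking. All of this stands, and it limits the point to a possibility.

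The reply is stronger still for the pathologists. Unstained sections go to a central laboratory and no route for the stiffness value is described. That part is a gap in the text without an identified channel, and it carries less weight than the operator part.

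What the reply does not remove is that a site could follow the plan to the letter and have a person who knows the stage choose position, trigger and repeats.

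A reader might go further and infer that operators did know the stage, that pathologists saw the stiffness values, or that the accuracy estimates are inflated. The documents support none of these. They do not describe what happened at the sites, and they contain no figure from which a bias could be derived. Any percentage shift in stiffness by stage would be an invented input.

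**Conclusion.** The point holds as an unstated safeguard. The visible text does not mask the FibroTouch operator to the biopsy stage, while its own provisions make knowledge of the stage at the scan possible. The possible consequence is stage-dependent bias in sensitivity, specificity and AUC, of unknown size and perhaps zero. Unstated masking of the pathologists is a secondary and weaker point.

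The conclusion assumes that Appendix 2 and the SOP do not already set masking. If they do, a cross-reference is enough. I would class this as a cheap improvement: it rests on the importance of masking to the study goal and on the low cost of adding it, not on a demonstrated effect.

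**What to change.** In Section VII and Section IX (III) items 5 to 7, state that:

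- the FibroTouch and FibroScan operators have no access to the IWRS stage entry or to any local or central pathology result until the stiffness measurement is saved;
- a different existing team member enters the stage;
- pathologists read coded slides without the stiffness value.

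Record the date and time of stage entry, scan and slide reading, so that accuracy can at least be described by test order. If repeat sets are logged, define the FibroTouch result as the first set that meets all of item 5's requirements: the A-, M- and E-signal criteria as well as an IQR-to-median ratio of at most 0.3. Reconcile the test order across inclusion criterion 3 and items 4, 5 and 7. If Appendix 2 or the SOP already provides masking, refer to it in the text.

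The cost is protocol wording, access rights, slide coding and some scheduling effort. The main burden is separating the registering and scanning roles at each site, which small sites may need to arrange. The fixed-operator rule stands only under FibroTouch, so the FibroScan operator has to be named explicitly. No added patients or procedures are needed.
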